7.5.2 Worsening Respiratory Status Categories

Worsening respiratory status will be categorized as follows:

- Early worsening: worsening respiratory status occurring ≤ 72 hours after birth
- Late worsening: worsening respiratory status occurring > 72 hours and ≤ 7 days after birth

7.6 Respiratory Support and Oxygen Delivery

Study subjects must be maintained on nCPAP from the time of randomization until they have completed delivery of lucinactant for inhalation as outlined in Section 5.4. The management of respiratory support (to include nCPAP) and oxygen delivery after the completion of lucinactant for inhalation delivery will be at the discretion of the study PI.

During nCPAP delivery subjects must be closely monitored for complications related to placement of the patient interface (eg, bi-nasal prongs). Assessment must include but not be limited to evaluation for the following conditions: bleeding, apparent obstruction of the nares, occlusion of interface requiring removal and replacement, nasal irritation (erythema of nares or septum, inflammation of nares or septum). Evidence of these conditions should be reported as an AE and treated in accordance with local institutional practice.

FiO₂ values (regardless of mode of delivery) will be recorded following randomization and will continue for 72 hours post randomization.

7.6.1 Emergent Respiratory Support

Emergent endotracheal intubation and mechanical ventilation, in accordance with local institutional guidance, must be initiated at any time if deemed necessary for subject safety. In such instances, the subject must be evaluated for worsening of respiratory status (Section 7.5.2).

Any clinical event indicating a need for mechanical ventilation, additional pressure support or increases in supplemental oxygen must be evaluated as a potential AE (Section 9) and reported in the study eCRF as such, if applicable.

7.6.2 Documentation During Primary and Extended Observation Period

From the time of randomization until completion of Study Day 7 the following must be evaluated and documented in the study eCRF:

1. Mechanical ventilation: date and time of initiation and discontinuation, the mode, mean airway pressure, respiratory rate, set tidal volume (if appropriate), and FiO₂
 - To be documented every 12 hours (\pm 1 hour) until mechanical ventilation has been discontinued for > 24 hours
2. Pressure support (to include nCPAP): date and time of initiation and discontinuation, PIP, respiratory rate, CPAP, flow rate, and FiO₂, as appropriate.
 - Primary Observation Period: document at 1, 3 (\pm 15 minutes), 6, 12 (\pm 1 hour), 18, 24, 36, and 48 hours (\pm 2 hours) post-randomization
 - Extended Observation Period: document every 12 hours (\pm 1 hour) until nCPAP has been discontinued for > 24 hours
3. Supplemental oxygen (FiO₂ > 21%): date and time of initiation and discontinuation, mode of delivery (eg, nasal cannula, oxygen hood), and FiO₂, as appropriate.

- After the administration of lucinactant for inhalation, FiO_2 must be documented every 12 hours (± 1 hour) until supplemental oxygen has been discontinued for > 24 hours

4. Intubation: the date and time of intubation for any reason must be documented.

If respiratory support or oxygen delivery is reinitiated following discontinuation, then parameters must again be captured every 12 hours until discontinuation.

7.6.3 Documentation During Final Observation Period

From Study Day 8 until the subject completes or withdraws from the study, the following must be evaluated and documented in the study eCRF:

- Intubation and mechanical ventilation: date and time of initiation and discontinuation
- Pressure support (to include nCPAP): date and time of initiation and discontinuation
- Supplemental oxygen: date and time of initiation and discontinuation, mode of delivery and FiO_2
- Intubation: the date and time of intubation for any reason

7.7 Criteria for Acute Respiratory Deterioration

Subjects must be closely monitored for signs and symptoms of acute respiratory deterioration throughout the study period. Any clinical signs of acute respiratory deterioration must be treated in accordance with local institutional practices and under the best medical judgment of the study PI.

Acute respiratory deterioration must be reported as an AE and, for study purposes, is defined by an increased respiratory rate or an observed increase in respiratory effort (work of breathing) plus at least one of the following criteria:

1. An $FiO_2 \geq 0.70$ or a sustained increase from baseline by ≥ 0.30 to maintain oxyhemoglobin saturation
2. A $PCO_2 > 70$ mm Hg or a progressive increase from baseline to ≥ 20 mm Hg above baseline and confirmed with a blood gas
3. Recurring episodes of bradycardia defined as a heart rate < 100 bpm for ≥ 20 seconds
4. A sustained apnea event, defined as apnea for at least 20 seconds in duration and meeting at least one of the following: (1) HR < 100 bpm, (2) desaturation (oxygen saturation $< 80\%$), (3) requirement for intermittent positive pressure breaths using inflating pressures

above the set CPAP pressure administered manually or mechanically through any patient interface

5. Endotracheal intubation for any reason (with the exception of elective surgical procedures)
6. Initiation of intermittent positive pressure breaths using inflating pressures above the set CPAP pressure administered manually or mechanically through any patient interface
7. nCPAP > 7 cm H₂O
8. Death while on study
9. The study PI determines that the subject has worsening respiratory status based on their best clinical judgment (Note: When medical judgment is the sole criteria for stopping therapy, a detailed narrative describing the clinical events and observations supporting the decision to stop therapy needs to be documented.)

8 EVALUATIONS BY VISIT

All of the following assessments will be performed until the time the subject completes the study (36 weeks PMA) or withdraws (Section 10.2).

A Schedule of Events representing the required testing procedures and the associated timeframe to be performed for the duration of the study is outlined in Appendix 2.

8.1 Screening Period

The following information will be obtained for each subject before study enrollment:

- A signed ICF
- Maternal history, to include (Section 7.2):
 - a) Rupture of membranes (time relative to birth, type)
 - b) Chorioamnionitis (clinical)
 - c) Antenatal steroids (number of doses, time relative to birth)
- Birth history, to include (Section 7.2):
 - a) Date and time of birth
 - b) Mode of delivery (vaginal, C-section)
 - c) Single or multiple birth (number)
 - d) Apgar score (assessed at 1 and 5 minutes)
 - e) Congenital anomaly
- Medical History (Section 7.2)
- Demographics, to include Section 7.4:
 - a) Sex
 - b) Race
 - c) Ethnic origin
 - d) Birth weight (grams) (Section 7.1.2)
 - e) Gestational age (weeks)
- Initial physical examination findings (Section 7.1.6)
- Inclusion and exclusion criteria (Sections 4.2 and 4.3)
- Chest radiograph (Section 7.1.8)
- Date and time of initial nCPAP or other type of controlled positive pressure ventilation

8.2 Primary Observation Period

The following will be documented for each randomized subject during the Primary Observation Period of the study (≤ 48 hours after randomization [T_0]):

1. Date and time (T_0) of randomization and the study dosing group assignment (Section 5.2.2)
2. The date and time of the initiation and completion of aerosol delivery (Section 5)
3. All AEs, including ADEs (Section 9)
Peri-dosing events (defined as an AE with an onset time ≤ 2 hours from the time of initiating administration of lucinactant for inhalation) may include but not be limited to:
 - Bradycardia (as noted by HR < 100 bpm for ≥ 20 seconds) (Section 7.1.1)
 - Desaturation (as noted by O₂ saturation $< 80\%$ for ≥ 20 seconds) (Section 7.1.3)
 - Gagging/regurgitation
 - Apnea (central, obstructive, or combined) (Section 7.1.1)
 - Pallor
 - Complications related to placement of bi-nasal prongs (bleeding, apparent obstruction of the nares, bi-nasal prongs occlusion requiring removal and replacement, nasal irritation).
4. Respiratory support and supplemental oxygen as outlined in Section 7.6
5. nCPAP settings (Section 5.4), (Section 7.6)
6. FiO₂ values (Section 7.1.4)
7. Signs and symptoms consistent with worsening of respiratory status (Section 7.5)
8. Vital signs and SpO₂ (Section 7.1.1, Section 7.1.3)
9. PCO₂ values (Section 7.1.5)
10. Chest radiograph, as applicable (Section 7.1.8)
11. Gastric liquid volume (Section 7.1.9)
12. Serum electrolytes (Section 7.1.7)
13. Defecation (initial 24 hours following randomization) (Section 7.1.10)
14. Concomitant medications (Section 7.3)
15. Technical performance of the device (Section 5.1.4)
16. The use of pacifiers

8.3 Extended Observation Period:

The following assessments are to be performed during the Extended Observation Period of the study (> 48 hours to ≤ 7 days after date of randomization). Daily measurements are to be obtained as close to 0800 as possible.

1. Assessment and documentation of respiratory support and supplemental oxygen (Section 7.6)
2. Signs and symptoms consistent with worsening of respiratory status (Section 7.5)
3. Vital signs (Section 7.1.1)
4. SpO₂ (Section 7.1.3)
5. Chest radiograph, as applicable (Section 7.1.8)
6. Incidence of AEs, including ADEs (Section 9)
7. Concomitant medications (Section 7.3)

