- Study Duration:** Overall study enrollment will be completed in approximately 7 months, with the last subject completing their last visit approximately 9 months from the time of the first subject enrolled.
- Subject participation will be from ≤ 20 hours following birth until 36 weeks PMA or discharge, whichever comes first.
- Method of Administration:** Subjects randomized to the active study arm will be administered an investigational drug-device combination product, lucinactant for inhalation, in conjunction with nCPAP. Reconstituted lyophilized lucinactant (reconstituted with sterile water for injection) will be aerosolized by the investigational device, ADS (using the CAG), and introduced into the nCPAP circuit. Those randomized to the control arm will continue to receive nCPAP alone.
- The exposure time will be based on the nominal dose, defined as the volume of lucinactant aerosolized by the ADS. Exposure, defined as the emitted dose, is the amount of lucinactant that is delivered at the connection to the patient interface by the ADS at a constant rate of flow. Because of losses that occur as the lucinactant aerosol travels from the ADS to the patient interface, the emitted dose is approximately 35% of the nominal dose. The theoretical inhaled dose, the fraction of the aerosolized lucinactant that the infant is exposed to that is likely to be inhaled, is estimated by product of the aerosol concentration, the minute ventilation of the infant, and the administration time of the aerosol.

Dosing Groups:

- Dosing Group I Active Arm (n = 8): 50 mg TPL/kg administered over 30 minutes in conjunction with nCPAP
1 Repeat dose of 50 mg TPL/kg administered over 30 minutes is allowed if repeat dosing criteria are met.
Control Arm (n = 8): Continuous nCPAP
- Dosing Group II Active Arm (n = 8): 75 mg TPL/kg administered over 45 minutes in conjunction with nCPAP
1 Repeat dose of 75 mg TPL/kg administered over 45 minutes is allowed if repeat dosing criteria are met.
Control Arm (n = 8): Continuous nCPAP
- Dosing Group III Active Arm (n = 8): 100 mg TPL/kg administered over 60 minutes in conjunction with nCPAP
1 Repeat dose of 100 mg TPL/kg administered over 60 minutes is allowed if repeat dosing criteria are met.
Control Arm (n = 8): Continuous nCPAP
- Dosing Group IV Active Arm (n = 8): 150 mg TPL/kg administered over 90 minutes in conjunction with nCPAP
1 Repeat dose of 150 mg TPL/kg administered over 90 minutes is allowed if repeat dosing criteria are met.

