2.2.3.3 Dose Exposure and Delivery

The inhaled doses for this dose escalation study are based on a previously conducted clinical study of aerosolized lucinactant (KL4-CPAP-01) that consisted of a theoretical inhaled dose of aerosolized lucinactant of approximately 72 mg TPL/kg over a 3 hour period for RDS prophylaxis in preterm neonates 28 to 32 weeks PMA (Section 1.3.1). The initial dose will be approximately one third of the theoretical inhaled dose of the previous study.

The theoretical inhaled dose can be estimated using the following equation:

$$\text{Inhaled Dose} = C \times \left(\frac{V_m}{kg} \right) \times T$$

Where: C = Aerosol concentration
Vm/kg = Minute ventilation per kg of body weight
T = Dose duration in minutes

- C: the aerosol concentration is calculated by dividing the emitted dose by the flow rate of the carrier gas used to drive the aerosol to the patient interface;
- Vm/kg : the subject's Vm can be calculated based on the patient's weight⁽¹⁴⁾, or based on direct neonatal lung function measurements of newborns⁽¹⁵⁾. [Table 2.2-1](#) shows the comparison of Vm values derived from these two sources;
- T: the duration of aerosol exposure in minutes is a modifiable, external factor that is determined by the target inhaled dose as a function of the CAG output; once this is known, the nominal dose can be calculated.

The emitted dose of the ADS is the product of the CAG output (1.2 ml/min), the concentration of the lucinactant (30 mg TPL/ml) and the fraction of the nominal dose that is delivered at the patient interface is 0.35:

$$\text{Emitted dose} = 1.2 \text{ ml/min} \times 30 \text{ mg TPL/ml} \times 0.35 = 12.6 \text{ mg TPL/min}$$

The aerosol concentration (C) is the emitted dose (12.6 mg TPL/min) divided by the carrier gas flow rate (3 L/min). This flow rate was chosen because it best represents the range of inspiratory flow rates observed in the target population.

$$C = \frac{12.6 \text{ mg TPL/min}}{3 \text{ L/min}} = 4.2 \text{ mg TPL/L}$$

Estimates of minute ventilation (Vm) within the range of body weights of preterm infants expected to enroll in the study are listed in [Table 2.2-1](#), based on the work of Bide, et al. and Bhutani, et al ^(14,15). When normalized to body weight, the Vm/kg is consistent across the range of weights at approximately 0.4 L/min/kg.

Table 2.2-1. Minute Ventilation Comparison Between Bide and Bhutani

Weight (g)	Bide et al.		Bhutani et al.	
	Vm		Vm (50 th percentile)	

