	(L/min/kg) ¹	(L/min)	(L/min/kg)	(L/min)
750	0.527	0.3954	0.4	0.3000
1000	0.499	0.4990	0.4	0.4000
1250	0.478	0.5977	0.4	0.5000
1500	0.462	0.6927	0.4	0.6000
1750	0.448	0.7847	0.4	0.7000
2000	0.437	0.8742	0.4	0.8000
2250	0.427	0.9616	0.4	0.9000
2500	0.419	1.0472	0.3	0.7500
2750	0.411	1.1312	0.3	0.8250

¹ Calculated

The four levels for the theoretical inhaled dose are 50, 75, 100, and 150 mg TPL/kg. By using these values, the dose duration (T) is calculated by dividing the target inhaled dose by the product of C (4.2 mg TPL/L) and Vm (0.4 L/min/kg). This calculation yields dose durations of 30, 45, 60 and 90 minutes to achieve target theoretical doses.

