5.3.2.1 ADP Set-up

Instructions for the proper set-up and connections of ADP components are provided in the ADS Operator’s Manual. Depending upon the dose, 1 or 2 ADPs will be required for each treatment.

The syringe is filled to maximum volume with the lucinactant suspension and placed in the syringe sleeve located in the ACU. To ensure full aerosol delivery, and proper functionality of

the device, it is imperative that the syringe is filled to the maximum volume and all air bubbles are removed before placement into the device.

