1.2.3 Safety Evaluations

The following measures are to be documented in the electronic case report form (eCRF) in accordance with timings outlined in study schedule:

1. Survival (date and time of death if applicable)
2. AEs, including ADEs
 - To include: nasal excoriations by examination (≥ 24 hours to ≤ 7 days following aerosol exposure) and evidence of lung air leak (especially pneumothorax)
 - To be categorized as a peri-dosing events if onset of event is ≤ 24 hours from the time of initiating administration of lucinactant for inhalation
3. Signs consistent with worsening respiratory status
4. Concomitant medications
5. Use of respiratory support and supplemental oxygen to include:

- Need for endotracheal intubation and mechanical ventilation
 - Need for intermittent positive pressure breaths using inflating pressures above the set CPAP pressure administered manually or mechanically through any patient interface
6. nCPAP and fraction of inspired oxygen (FiO₂) requirements
 7. Complications of prematurity (ie, IVH, periventricular leukomalacia [PVL], pulmonary hemorrhage, NEC, patent ductus arteriosus [PDA], sepsis, ROP, BPD)
 8. Physical examinations
 9. Tolerability of lucinactant for inhalation
 10. Incidence leading to withdrawal from study
 11. Incidence of air leak
 12. Assessments of the following:
 - a) PCO₂
 - b) Serum electrolyte measurements
 - c) Body weight
 - d) Vital signs
 - e) Gastric liquid volume
 - f) Defecation
 - g) Oxygen (O₂) saturation, as determined by pulse oximetry (SpO₂)
 - h) Chest radiography, as applicable

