¹⁰ Peri-dosing events are defined as any AE with an onset time ≤ 2 hours from the time of initiating study treatment.

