6.4.1 Peri-Dosing AEs

The incidence of peri-dosing events (bradycardia, desaturation, and vomiting) will be summarized. In addition, the incidence of complications related to the placement of bi-nasal prongs (bleeding, apparent obstruction to the nares, occlusion of the prongs, nasal irritation, and other) will be summarized. Peri-dosing events and complications related to the placement of the prongs will also be summarized with all adverse events.

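### The 2-hour peri-dosing window contains 30 to 90 minutes of aerosol time depending on the dose, so SAP Table 6.1 should separate in-dose from post-dose onset

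*Protocol*

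**What the plan says.** The Protocol anchors the peri-dosing category on the start of aerosol. Section 8.2 describes it as "an AE with an onset time ≤ 2 hours from the time of initiating administration of lucinactant for inhalation", and Section 3.3 and Appendix 2 use the same 2 hours. The SAP agrees in its Executive Summary and in the notes to its study schedule (2.2.4): "Peri-dosing events are defined as any AE with an onset time ≤ 2 hours from the time of initiating study treatment". SAP 1.2.3 differs: "To be categorized as a peri-dosing events if onset of event is ≤ 24 hours from the time of initiating administration".

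The time on aerosol rises with the dose. On the four target doses, Protocol 2.2.3.3 says: "This calculation yields dose durations of 30, 45, 60 and 90 minutes to achieve target theoretical doses". The top group is to receive "150 mg TPL/kg administered over 90 minutes in conjunction with nCPAP".

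On analysis, SAP 6.4.1 says: "The incidence of peri-dosing events (bradycardia, desaturation, and vomiting) will be summarized". The output is Table 6.1. The SAP's Executive Summary places peri-dosing events among the key safety and tolerability endpoints. Neither document separates onset during aerosol from onset after it, or says how the window runs after a repeat dose.

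**The concern.** The window has a fixed length, but the treatment inside it does not. As the dose rises, more of the 2 hours is spent on aerosol and less remains afterwards. An event that starts 60 minutes after aerosol ends is peri-dosing at 50 mg TPL/kg (90 minutes from the start) and not at 150 mg TPL/kg (150 minutes from the start).

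The Protocol's own schedule shows how this could matter. Under Section 7.1.9, enteral feeds are held until at least 1 hour after completion. Vomiting is one of the events SAP 6.4.1 names. Vomiting at the first permitted feed could count in Groups I and II, would sit on the limit in Group III, and could not count in Group IV.

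At stake is how acute tolerability is read across doses. Determining the maximum tolerated dose is a secondary objective (Protocol 3.2, SAP 1.2.2), and SAP 1.1.2 says the results will assist dose selection. Table 6.1 is the only planned table that ties AEs to the time of dosing.

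**Working it through.** **Inputs.** From Protocol 2.2.3.3: device output 1.2 ml/min, concentration 30 mg TPL/ml, delivered fraction 0.35, carrier flow 3 L/min, minute ventilation 0.4 L/min/kg. From Protocol 8.2: a window of 120 minutes from the start. From Protocol 5.3.2: a 60 ml syringe per delivery pack.

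**Reproducing the plan's durations.** Aerosol concentration = 1.2 × 30 × 0.35 / 3 = 4.2 mg TPL/L. Duration = dose / (4.2 × 0.4), which gives 29.8, 44.6, 59.5 and 89.3 minutes. These round to the stated 30, 45, 60 and 90.

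**Splitting the window.** With T the duration, post-dose time = 120 − T, in-dose share = T / 120, and earliest feed = T + 60 minutes from the start.

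| Group | T (min) | Post-dose time in window (min) | In-dose share | Earliest feed (min from start) |
|---|---|---|---|---|
| I | 30 | 90 | 25% | 90 |
| II | 45 | 75 | 37.5% | 105 |
| III | 60 | 60 | 50% | 120 |
| IV | 90 | 30 | 75% | 150 |

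The aerosolized volume is 1.2 × T = 36, 54, 72 and 108 ml. Groups III and IV exceed one syringe, which fits Protocol 5.3.2.1: "Depending upon the dose, 1 or 2 ADPs will be required for each treatment". Any pause for the changeover makes 60 and 30 post-dose minutes upper limits.

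**Effect on Table 6.1 if dose itself does nothing.** The documents give no event rates, so these hazards are assumptions. With hazard a per hour during aerosol and b per hour after it, both the same at every dose, P(event in window) = 1 − exp(−[a × T/60 + b × (120 − T)/60]).

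| Assumed hazards per hour | I | II | III | IV |
|---|---|---|---|---|
| a = 0.3, b = 0.1 | 25.9% | 29.5% | 33.0% | 39.3% |
| a = 0.1, b = 0.3 | 39.3% | 36.2% | 33.0% | 25.9% |
| a = b = 0.1 | 18.1% | 18.1% | 18.1% | 18.1% |

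For example, Group I in the first row is 1 − exp(−[0.3 × 0.5 + 0.1 × 1.5]) = 1 − exp(−0.3) = 25.9%. With 8 infants per active group, 25.9% and 39.3% are 2.1 and 3.1 expected infants.

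**Dependence on the 24-hour wording.** If SAP 1.2.3 prevailed, post-dose time would be 24 hours − T = 23.5, 23.25, 23.0 and 22.5 hours. The imbalance would nearly vanish.

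**Moving the anchor to the end of aerosol.** A window ending 2 hours after completion equalizes post-dose time, but total time becomes T + 120 = 150, 165, 180 and 210 minutes. That exchanges one inequality for another.

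**The case against.** The strongest reply is that the definition answers a coherent question: what happens within 2 hours of starting this regimen. Longer time on aerosol is part of the higher dose, and every group is observed for the same 120 minutes. That stands. A reader might infer that the dose columns cannot be compared at all. The documents do not support this, because total time at risk is equal and only its composition changes.

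A reader might also infer that the window makes the highest dose look safer. Suppose the risk in the 2 hours after aerosol ends were 20% at every dose, with onset spread evenly. The window would then capture 20% × (90, 75, 60, 30)/120 = 15%, 12.5%, 10% and 5%. Those are not Table 6.1 incidences, because they omit in-dose events, which have more time to occur as the dose rises. The net direction depends on hazards that the documents do not give.

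Nor does the window control escalation. The enrollment-hold rules (Protocol 6.2, SAP 7.2) use related SAEs and related deaths within 12 hours. The safety review committee also sees all AEs, together with dosing-related AEs as defined in Protocol Appendix 1, which has no 2-hour limit. Events outside the window remain in the all-AE tables, and SAP 6.4 plans no comparison of AEs between treatment groups.

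These points limit the concern without removing it. The all-AE tables have no split by time from dosing, and AEs are collected to 36 weeks PMA. Protocol Section 9 makes bradycardia, desaturation, sustained apnea and air leak AEs of special interest through the 48-hour primary observation period, but the SAP lists no table for that period. The absence of a formal comparison does not prevent adjacent dose columns being read against each other, which judging a maximum tolerated dose requires.

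**Conclusion.** The concern holds as a limit on how Table 6.1 can be interpreted. Under the 2-hour definition, in-dose time rises from 30 to 90 minutes and post-dose time falls from 90 to 30 minutes over the four groups. An apparent dose trend, or its absence, could therefore come from the mix alone. A threefold difference between the assumed hazards moves incidence by about 13 percentage points (39.3 − 25.9 = 13.4) in either direction, or roughly one infant in eight. If in-dose and post-dose hazards are equal, nothing is distorted.

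The conclusion rests on two conditions: that the 2-hour and 24-hour wordings are reconciled to 2 hours, which is what most of the text says, and that doses run for their planned durations. It is a worthwhile, inexpensive improvement to reporting. It is not a flaw in the dose-escalation safeguards.

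**What to change.** First reconcile SAP 1.2.3 with the 2-hour definition used elsewhere. If 2 hours is confirmed, keep that definition and its existing row, because Protocol Section 3 wants endpoints that can be pooled with Study 03-CL-1201. Then add to SAP 6.4.1 and Table 6.1, for each active group:

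- **Onset during aerosol**, with minutes of exposure and events per hour, because in-dose time differs by dose. For eight complete initial doses the exposure would be 8 × 0.5, 0.75, 1 and 1.5 hours = 4, 6, 8 and 12 infant-hours.
- **Onset from aerosol completion to 2 hours after completion**, which is the same interval in every group (8 × 2 = 16 infant-hours if all are observed).

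Show the initial and repeat dose separately. Use actual stop times for doses ended early, and state beforehand how a pause for a syringe changeover is counted.

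The cost is SAP wording and extra rows with small counts. Aerosol start and completion times (Protocol 8.2) and AE onset times (Protocol Section 9) are already collected, so no new data and no change to the conduct of the trial are needed.
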